11.0 LABELING, PACKAGING, STORAGE AND RETURN OF CLINICAL SUPPLIES

11.1 Standard Treatment

BCG will be utilized as the product of standard treatment for this protocol for superficial bladder cancer. The Investigator will take appropriate steps to ensure that appropriate records are maintained regarding the use of BCG in the study. BCG will be supplied through commercial sources and the supply, storage, handling, distribution, and usage of BCG will be in accordance with local practice and any applicable laws and regulations, including this protocol.

Clinical Supplies will be provided through commercial sources. The approved package labeling will be utilized for the preparation and storage and handling of BCG.

11.2 Investigational Product

The Investigator shall take responsibility for and shall take all steps to maintain appropriate records and ensure appropriate supply, storage, handling, distribution and usage of investigational product in accordance with the protocol and any applicable laws and regulations.

Clinical Supplies will be provided by Merck as summarized in Table 9.

Table 9: Product Descriptions

Product Name & Potency	Dosage Form
MK-3475 100 mg/ 4mL	Solution for Injection

11.3 Packaging and Labeling Information

Clinical supplies will be affixed with a clinical label in accordance with regulatory requirements.

11.4 Clinical Supplies Disclosure

This trial is open-label; therefore, the subject, the trial site personnel, the Sponsor and/or designee are not blinded to treatment. Drug identity (name, strength) is included in the label text; random code/disclosure envelopes or lists are not provided.

Product: MK-3475

Protocol/Amendment No.: Amendment 5, 21 October 2019

11.5 Storage and Handling Requirements

Clinical supplies must be stored in a secure, limited-access location under the storage conditions specified on the label.

Receipt and dispensing of trial medication must be recorded by an authorized person at the trial site.

Clinical supplies may not be used for any purpose other than that stated in the protocol.

11.6 Returns and Reconciliation

The Investigator or designee is responsible for keeping accurate records of the clinical supplies received from Merck, the amount dispensed to and returned by the subjects and the amount remaining at the conclusion of the trial.

Upon completion or termination of the study, all unused and/or partially used investigational product will be destroyed at the site per institutional policy. It is the Investigator's responsibility to arrange for disposal of all empty containers, provided that procedures for proper disposal have been established according to applicable federal, state, local, and institutional guidelines and procedures, and provided that appropriate records of disposal are kept.

12.0 ADMINISTRATIVE AND REGULATORY DETAILS

12.1 Confidentiality

The Investigator and Sponsor of the study must adhere to all applicable data privacy and confidentiality laws and regulations (i.e. HIPAA). Those applicable include institutional, state, and Federal Law. It is the responsibility of the Investigator and Sponsor to ensure the subject data as well as sensitive study information is handled according to applicable guidelines and laws. Appropriate authorization and consent for use, disclosure, or transfer of protected health information must be obtained.

Subject names will not be recorded on the CRF. Only the subject number and subject's initials will be recorded, where permitted. If the subject's name appears on any other document (e.g., pathology report), it must be obliterated on the copy of the document as appropriate. Study data stored on a computer will be stored in accordance with local data protection laws. The subjects will be informed that representatives of the sponsor or its designee, IRB, and regulatory authorities may inspect their medical records to verify the information collected, and that all personal information made available for inspection will be handled in strictest confidence and in accordance with local data protection laws.

12.2 Compliance with Financial Disclosure Requirements

All participating Investigators must have on file a completed clinical Investigator Financial Disclosure Form. The form must sufficiently detail any financial interests or arrangements that may apply. For the purposes of this study, the Financial Disclosure Form required by the

Product: MK-3475

Protocol/Amendment No.: Amendment 5, 21 October 2019

Springfield Committee for Research Involving Human Subjects will be utilized. A clinical Investigator is defined as any Investigator or Sub-Investigator who is directly involved in the treatment or evaluation of research subjects (this includes the spouse and each dependent child of the clinical Investigator). All new study personnel must submit a completed Financial Disclosure Form with the IRB application. Investigators are required to report any changes of their financial information/status as previously reported while the study is ongoing and for a period of 1 year after the completion of the study.

12.3 Compliance with Law, Audit and Debarment

The Investigator, Sub-Investigator and Sponsor of the study are required to comply with and adhere to all local, state, and federal law that is applicable to the study.

12.3.1 Sponsor Audits

At any point throughout the study, the Sponsor may visit the study site to conduct an audit of the study. The purpose of this visit generally will be to determine the Investigator's adherence to the Protocol, applicable regulations, and the Sponsor's procedures, as well as assessing the accuracy of the study data.

12.3.2 Inspection by Regulatory Authorities

A regulatory authority may visit the Investigator/Sponsor to conduct an inspection of the study and the site. The site Investigator and staff are expected to cooperate with the inspectors and allow access to all source documents supporting the CRFs and other study-related documents.

12.4 Compliance with Laws and Regulations

The proposed study is to be conducted according to federal regulation including:

Please refer to: Code of Federal Regulations, Title 21:
<http://www.accessdata.fda.gov/scripts/cdrh/cfdocs/cfcfr/CFRSearch.cfm>

Code of Federal Regulations, Title 45 Part 46

12.4.1 Compliance with Trial Registration and Results Posting Requirements

Under the terms of the Food and Drug Administration Modernization Act (FDAMA) and the Food and Drug Administration Amendments Act (FDAAA), the Sponsor of the trial is solely responsible for determining whether the trial and its results are subject to the requirements for submission to the Clinical Trials Data Bank, <http://www.clinicaltrials.gov>. Information posted will allow subjects to identify potentially appropriate trials for their disease conditions and pursue participation by calling a central contact number for further information on appropriate trial locations and trial site contact information.

Product: MK-3475

Protocol/Amendment No.: Amendment 5, 21 October 2019

12.4.2 Protocol Adherence

IRB approval and all materials approved by the IRB for this study, including the subject ICF and recruitment materials, must be maintained by the Investigator and made available for inspection. Each Investigator must adhere to the Protocol as described in this document and agree that changes to the Protocol, with the exception of medical emergencies, must be discussed and approved by the IRB. The Investigator is responsible for enrolling subjects who have met the inclusion and exclusion criteria. The IRB granting approval must be notified of all changes in and deviations from the Protocol that may increase risk to the subject, and/or may adversely affect the rights of the subject or validity of the investigation.

12.5 Quality Management System

Qualified staff of the Sponsor will monitor the study according to a pre-arranged monitoring plan. Monitoring of the study will include:

- Evaluation of study progress
- Verification of CRF accuracy and completeness
- Resolution of inconsistencies in study records
- Assurance of protocol requirements and investigator's obligations are fulfilled
- Assurance of compliance with applicable laws and regulations

Study monitors will periodically review all CRFs and supporting source documentation of participating subjects. The CRFs and supporting documentation must remain up to date and available to the study monitor as arranged. CRF data entry will be verified to correspond with source documentation (laboratory, imaging, pathology reports, etc.) and reviewed for completeness. Data discrepancies will be identified and reported to the Investigator and site staff.

Protocol deviations will be identified and recorded on a deviation log.

12.6 Data Management

The Investigator will be provided with a CRF for each subject. Entries made in the CRF must be verifiable against source documents; any discrepancies should be explained and documented. The Investigator will be responsible for reviewing all data and CRF entries and will sign and date the designated pages in each subject's CRF, verifying that the information is true and correct. The Investigator is responsible for the review and approval of all responses.

Data management will be performed from CRFs. All CRF data will be entered into a validated database. All data entry, verification, and validation will be performed in accordance with the current standard operating procedures of the Sponsor.

12.6.1 Retention of Records

The Investigator must maintain all documentation relating to the study for a period of 2 years after the last marketing application approval, or if not approved, 2 years following the

Product: MK-3475

Protocol/Amendment No.: Amendment 5, 21 October 2019

termination of the test article for investigation. State of IL Law requires retention of materials for 6 years following completion of study. If it becomes necessary for a regulatory authority to review any documentation relating to the study, the Investigator must permit access to such records.

All CRFs will be maintained or made available at the site in compliance with applicable record retention regulations.

APPENDIX A

ECOG PERFORMANCE STATUS

Grade	Description
0	Normal activity. Fully active, able to carry on all pre-disease performance without restriction.
1	Symptoms, but ambulatory. Restricted in physically strenuous activity, but ambulatory and able to carry out work of a light or sedentary nature (e.g., light housework, office work).
2	In bed <50% of the time. Ambulatory and capable of all self-care, but unable to carry out any work activities. Up and about more than 50% of waking hours.
3	In bed >50% of the time. Capable of only limited self-care, confined to bed or chair more than 50% of waking hours.
4	100% bedridden. Completely disabled. Cannot carry on any self-care. Totally confined to bed or chair.
5	Dead.

* As published in Am. J. Clin. Oncol.: *Oken, M.M., Creech, R.H., Tormey, D.C., Horton, J., Davis, T.E., McFadden, E.T., Carbone, P.P.: Toxicity And Response Criteria Of The Eastern Cooperative Oncology Group. Am J Clin Oncol 5:649-655, 1982.* The Eastern Cooperative Oncology Group, Robert Comis M.D., Group Chair.

Product: MK-3475

Protocol/Amendment No.: Amendment 5, 21 October 2019

APPENDIX B

Calculation of CKD-EPI GFR

<http://www.qxmd.com/calculate-online/nephrology/ckd-epi-egfr>

The CKD-EPI (Chronic Kidney Disease Epidemiology Collaboration) equation was developed in an effort to create a formula more precise than the MDRD formula, especially when actual GFR is > 60 mL/min per 1.73 m². Researchers pooled data from multiple studies to develop and validate this new equation. They randomly divided 10 studies, which included 8,254 participants, into separate data sets for development and internal validation. Sixteen (16) additional studies, which included 3,896 participants, were used for external validation. The CKD-EPI equation performed better than the MDRD (Modification of Diet in Renal Disease Study) equation, especially at higher GFR, with less bias and greater accuracy. When looking at NHANES (National Health and Nutrition Examination Survey) data, the median estimated GFR was 94.5 mL/min per 1.73 m² vs. 85.0 mL/min per 1.73 m², and the prevalence of chronic kidney disease was 11.5% versus 13.1%. The CKD-EPI equation, expressed as a single equation, is:

$$\text{GFR} = 141 \times \min(\text{Scr}/\kappa, 1)^\alpha \times \max(\text{Scr}/\kappa, 1)^{-1.209} \times 0.993^{\text{Age}} \times 1.018 \text{ [if female]} \times 1.159 \text{ [if black]}$$

Where Scr is serum creatinine (mg/dL), κ is 0.7 for females and 0.9 for males, α is -0.329 for females and -0.411 for males, min indicates the minimum of Scr/ κ or 1, and max indicates the maximum of Scr/ κ or 1.

Stevens LA et al. [Comparative Performance of the CKD Epidemiology Collaboration \(CKD-EPI\) and the Modification of Diet in Renal Disease \(MDRD\) Study Equations for Estimating GFR Levels Above 60 mL/min/1.73 m²](#). *AJKD* 56(3):486-495.

Product: MK-3475

Protocol/Amendment No.: Amendment 5, 21 October 2019

APPENDIX C

TICE® BCG Package Insert

<http://www.fda.gov/downloads/BiologicsBloodVaccines/Vaccines/ApprovedProducts/UCM163039.pdf>

Product: MK-3475

Protocol/Amendment No.: Amendment 5, 21 October 2019

Appendix D

Questionnaire

AUA SYMPTOM SCORE

Last Name	First Name	Date

Highlight or bold or change font color of the response correct for you and type in your score in the far right box for all SEVEN questions.

1. **Incomplete emptying:** Over the past month, how often have you had a sensation of not emptying your bladder completely after you finished urinating?

Not at all	Less than 1 time in 5	Less than half the time	About half the time	More than half the time	Almost always	Your Score
0	1	2	3	4	5	

2. **Frequency:** Over the past month, how often have you had to urinate again less than 2 hours after you finished urinating?

Not at all	Less than 1 time in 5	Less than half the time	About half the time	More than half the time	Almost always	Your Score
0	1	2	3	4	5	

3. **Intermittency:** Over the past month, how often have you found that you stopped and started again several times when you urinated?

Not at all	Less than 1 time in 5	Less than half the time	About half the time	More than half the time	Almost always	Your Score
0	1	2	3	4	5	

4. **Urgency:** Over the past month, how often have you found it difficult to postpone urination?

Not at all	Less than 1 time in 5	Less than half the time	About half the time	More than half the time	Almost always	Your Score
0	1	2	3	4	5	

5. **Weak-stream:** Over the past month, how often have you had a weak stream?

Not at all	Less than 1 time in 5	Less than half the time	About half the time	More than half the time	Almost always	Your Score
0	1	2	3	4	5	

6. **Straining:** Over the past month, how often have you had to push or strain to begin urination?

Not at all	Less than 1 time in 5	Less than half the time	About half the time	More than half the time	Almost always	Your Score
0	1	2	3	4	5	

7. **Nocturia:** Over the past month or so, how many times did you get up to urinate from the time you went to bed until the time you got up in the morning?

None	1 time	2 times	3 times	4 times	5 or more times	Your Score
0	1	2	3	4	5	

Add up your scores for total AUA score = _____

Quality of Life Due to Urinary Symptoms: If you were to spend the rest of your life with your urinary condition just the way it is now, how would you feel about that? (Bold, Highlight or Underline)

Delighted Pleased Mostly satisfied Mixed Mostly dissatisfied Unhappy Terrible

Product: MK-3475

Protocol/Amendment No.: Amendment 5, 21 October 2019

Appendix E

CTCAE 4.0

http://evs.nci.nih.gov/ftp1/CTCAE/CTCAE_4.03_2010-06-14_QuickReference_5x7.pdf

Product: MK-3475

Protocol/Amendment No.: Amendment 5, 21 October 2019

Product: MK-3475

Protocol/Amendment No.: Amendment 5, 21 October 2019

Appendix F

Basic Science Correlates

Objective 1. Staining for PD-1, PDL-1, and CD3 in bladder tissue samples obtained at initial tumor resection and on follow up biopsies

Immunohistochemistry for PD-1, PD-L1, and CD3 in tissue from pretreatment biopsy and tumor resection will be performed to investigate the association between tissue expression of these markers and response to MK-3475. When preparing and submitting slides, newly cut sections will be utilized to ensure stability of the PD-L1 epitope. Staining for immunohistochemistry for markers of interest will involve baking formalin fixed paraffin embedded tissue sections for 45 minutes at 60 °C, then deparaffinized and rehydrated with serial passage through changes of xylene and graded ethanols. All slides will be subjected to heat induced epitope retrieval in either Envision FLEX Target Retrieval Solution, High pH (cat K8012, Dako, Carpinteria CA) or Target Retrieval Solution, pH 6.1 (cat S1699, Dako). Endogenous peroxidase in tissues will be blocked by incubation of slides in 3% hydrogen peroxide solution prior to incubation with primary antibody (anti-PD-L1 clone 22C3, Merck Research Laboratories, Palo Alto CA; anti-PD-1 clone NAT105, Cell Marque, Rocklin CA; or anti-CD3 clone F7.2.38, Dako) for 60 minutes. Antigen-antibody binding will be detected using polymer-based methods and visualized by application of 3,3' diaminobenzidine (DAB) chromogen (K4368, Dako). Stained slides will be counterstained with hematoxylin and coverslipped for review and scoring by a pathologist employing a semiquantitative 0-5 scale.

Specimens collected from biopsy (formalin fixed tissue blocks and slides) obtained at baseline (utilizing the specimen ICF form or the main study ICF) and Week 19 (main study ICF) will be utilized for the completion of Basic Science Correlates, Objective 1.

Objective 2. Whole exome sequencing of germline DNA and formalin fixed, paraffin embedded tissue on all patients. Correlation will be made to mutations and treatment outcomes.

The study Investigators are submitting a protocol that allows for DNA collection from genitourinary cancer patients. The same protocol will allow for collection of clinical data and DNA sequencing using next generation technology from patients who received MK-3475. Pathology reports from pre- and post-MK-3475 tumor resections and biopsies will be obtained. Response/no response to MK-3475 will be ascertained from the collected clinical data using definitions of response agreed on for high risk superficial bladder cancer. Germline DNA from patients with a complete set of data will be sequenced using next generation sequencing (exome sequencing at 40x) provided by industrial vendors (such as www.edgebio.com). Data from next generation sequencing will be analyzed using software provided by Ingenuity Inc. (www.ingenuity.com). Variants will be analyzed both in an agnostic and non-agnostic manners. Any genes reported in the literature to be associated with response to PDL-1 therapy will be examined to agnostically identify variants within these genes shared between responders/no responders to MK-3475 at a significant level. In addition, genetic variants common to responders/non responders and unrelated to genes identified previously in the literature as being

Product: MK-3475

Protocol/Amendment No.: Amendment 5, 21 October 2019

related to PDL-1 response will be examined (non-agnostic analysis). Such non-agnostic variants will be also considered as important targets for biomarker development if they are significantly associated with response/no response to treatment. Variants associated with response/no response will be then validated in the discovery cohort using sequenome analysis (www.sequenome.com) as agreed upon in the scientific methodology of such studies to avoid replicating variants that do not actually exist in the sampled DNA.

Specimens (including tumor and surrounding normal tissue, whole blood, serum, and urine) will be collected for future unspecified research if the subject agrees to collection and storage for future unspecified research. Specimens may come from subjects fully enrolled in the treatment portion of the study at baseline and Week 19. Specimens may also be obtained from subjects who have declined the treatment portion of the study or were ineligible, but gave permission for use of specimens despite not being enrolled into the treatment portion of the study. The specimens will be stored until completely utilized or for 50 years, whichever occurs first. These specimens will be utilized for completion of Basic Science Correlatives, Objective 2 if funding is secured or for other studies which may become apparent throughout the study, for example, development of a urine based assay for response assessment. Not all studies have been identified at this time.

Objective 3. Immune-profiling of bladder exudate and blood from patients treated with combination of BCG and pembrolizumab for high risk transitional cell carcinoma of the bladder

Bladder cancer is the fifth most common cancer in the United States.(1) The majority of diagnoses are non-muscle invasive bladder cancer (NMIBC), however a significant proportion of these cases will recur and some will ultimately become muscle invasive.(2) Thus, prevention of post-transurethral resection of bladder tumor (TURBT) recurrence of intermediate risk NMIBC would represent a major step towards reduction of bladder cancer mortality. Intravesical instillation of BCG represents first line treatment for NMIBC and is effective in preventing recurrence of superficial disease.(3) This is thought to elicit an immune reaction and the release of cytokines that active an immune response from neutrophils, macrophages, and T cells.(3) Recently, there have been advances in the treatment of advanced bladder tumors with agents targeting the programmed cell death protein (PD-1)/programmed cell death ligand (PDL-1) checkpoint pathway.(4) By blocking this pathway, a greater antitumor response by T cells is created resulting in increased bladder cancer cell immune mediated destruction.(5) We have a phase I clinical study examining the results of combining pembrolizumab, a monoclonal anti-PD1 antibody, with BCG treatments. In these patients, we have collected both urine and blood pre- and post-treatment. The urine in these patients contains the bladder inflammatory exudate that developed during treatment. **We hypothesize that the understanding of how combined BCG and pembrolizumab treatment affect the local (bladder exudate in urine) and systemic (blood) immune environment could be obtained from immune-profiling bodily fluids of our trial patients.**

Our collaborator, [name] from IncellDx has developed a high parameter flow cytometry assay for immune profiling in solid tumors and urine. In a lung study that combined primary tumor immune profiling and Circulating Tumor Cell (CTC) analysis, they were able to

Product: MK-3475

Protocol/Amendment No.: Amendment 5, 21 October 2019

identify both drug targets in the primary tumors and factors in the primary tumor that diminished immune control of tumor cells that led to detection of CTCs especially CTCs expressing PD-L1. We will use the patient samples derived from our phase I study and perform high parameter (>20 markers) analysis of urine and blood samples, below, both pre- and post-treatment to quantify the

355nm		405nm		488nm		561nm		638nm	
Specificity	Fluor	Spec	Fluor	Spec	Fluor	Spec	Fluor	Spec	Fluor
CD8	BUV496	CD103	BV421	PanCK	AF488	FoxP3	PE	PD-L1	AF647
CD4	BUV661	TIM3	BV605	PD-1	BB700	CD19	PE-Dazzle594	CCR5	AF700
CD45	BUV805	CD56	BV650			CD3	PE-Cy5	HLA-DR	APC/Fire750
CCR5	BUV385	LAG-3	BV711			CTLA-4	PE-Cy7		
		CD14	BV786						

immune cell sub-populations to create an immune profile. Furthermore, we will analyze serum cytokines to further establish immune response in patients. We will also compare the immune profiles for treatment responders and non-responders to determine if there are biomarkers for predicting response to this combined treatment modality much like we had done previously to identify immune control in the lung (below).

We will use the patient samples derived from our phase I study and perform FACS analysis to sort urine and blood samples, both pre- and post-treatment, into immune cell sub-populations to create an immune profile. Furthermore, we will analyze serum cytokines to further establish

Product: MK-3475

[figure not shown]
Protocol/Amendment No.: Amendment 5, 21 October 2019

immune response in patients. We will also compare the immune profiles for treatment responders and non-responders to determine if there are biomarkers for predicting response to this combined treatment modality.

[figure not shown]

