5.8 Clinical Criteria for Early Trial Termination

Early trial termination will be the result of the criteria specified below:

1. Quality or quantity of data recording is inaccurate or incomplete
2. Poor adherence to protocol and regulatory requirements
3. Incidence or severity of adverse drug reaction in this or other studies indicates a potential health hazard to subjects

Stopping Rules:

The number of patients (15) planned for this study is not sufficient to represent the population as a whole nor is it sufficient to complete a powerful statistical analysis.

The first 3 subjects will be treated at 100 mg every 3 weeks for 6 cycles. If one subject of the three subjects requires the dose of MK-3475 be withheld or discontinued, the 100 mg cohort will be expanded to 6 subjects. If two out of three or two out of six subjects

develop toxicity that requires the dose to be withheld or discontinued, the dose will be not be escalated to 200 mg MK-3475 every 3 weeks. All remaining subjects will be treated at 100 mg MK-3475 every 3 weeks for 6 cycles.

For study subject safety, if there is any fatal toxicity or morbidity event related to the study treatment or procedures, or if one or more of the 15 subjects treated experience a grade 4 toxicity, then subject accrual will be suspended and all data pertaining to the events will be reviewed by the Study Investigators and Data Safety Review Team to determine if there is the need for any corrective actions.

Once that review is completed and any appropriate action is taken, subject accrual will begin again, if the Data Safety Review Team members have approved continuation of the study. If there is a second fatal treatment/morbidity event related to the study treatment or procedures, the study will be terminated. If 4 of 15 subjects experience grade 4 toxicities, the accrual will be suspended and reviewed for added appropriate measures. If 5 subjects experience grade 4 toxicity, the study will be terminated.

Non-local safety reports will be evaluated as they are received. Tabulations of the reports will be provided to the Data Safety Review Team with access to the full reports for completeness of review.

4. Plans to modify or discontinue the development of the study drug

In the event the investigational product is no longer available, ample notification will be provided so appropriate adjustments to subject treatment can be made.

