For primary objective 1, the proportion of patients with each AE will be reported along with the NCI CTCAE Grade of the AE. The Quality of Life Questionnaire, which includes one question with seven categorical responses, will be described with frequencies and percentages. The American Urologic Association Symptoms Index Questionnaire, which includes seven questions each with a numerical score between 0 and 5 as well as a final numerical sum of all responses, will be described with measures of central tendency and dispersion. Due to the questionnaires being given at three time points (Pre-treatment, Mid-treatment, and Post-treatment), the responses may be analyzed to look for longitudinal effects over time for specific variables of interest with repeated measures ANOVA to evaluate changes and control for individual differences (*although this would be very low power due to n=15*).

For the secondary objective, subjects will be assessed at 19 weeks, 3 months, 12 months, and 24 months post treatment completion for complete response. The outcome endpoint will be complete response status at 19 weeks, 3 months, 12 months, and 24 months post treatment to measure complete response, recorded as yes or no and summarized as proportions and a percent.

Product: MK-3475

Protocol/Amendment No.: Amendment 5, 21 October 2019

These proportions/percent will be reported, but no statistical analysis will be performed as this is a single arm phase I study, and no control group is available for direct comparison.

For the exploratory objectives, Pearson or Spearman's rank correlation coefficient will be used to estimate correlations between expression level change and treatment outcome, as well as the correlations between mutation presence and treatment outcome.

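### The exome screen in Appendix F selects variants by an undefined significance rule with no error control across the variants tested, and the Sequenom step is not designed to remove chance associations

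*Combined protocol and SAP*

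**What the plan says.** Appendix F, Objective 2 sequences germline DNA and tumour tissue and compares variants between responders and non-responders in two parts. (The appendix's labels agnostic and non-agnostic run opposite to common usage, so they are not used here.)

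- **Literature genes.** The search is for "variants within these genes shared between responders/no responders to MK-3475 at a significant level". The level is not given.
- **All other variants.** These "will be also considered as important targets for biomarker development if they are significantly associated with response/no response to treatment". No test, level or multiplicity rule is given.

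The next sentence begins "Variants associated with response/no response will be then validated in the discovery cohort using sequenome analysis" and ends with its purpose: "to avoid replicating variants that do not actually exist in the sampled DNA".

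Section 10.1 adds only the method. It says "Pearson or Spearman's rank correlation coefficient will be used to estimate correlations between expression level change and treatment outcome" and applies the same coefficients to mutation presence against outcome. It says nothing about significance or multiple testing for this objective.

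On numbers, Appendix F says "Germline DNA from patients with a complete set of data will be sequenced using next generation sequencing (exome sequencing at 40x", with no count. Section 5.8 says "The number of patients (15) planned for this study is not sufficient to represent the population as a whole". Section 3.3 lists the sequencing as exploratory, and Appendix F makes it conditional on funding. Section 4.2.3.2 says that the biomarker work, genetic markers included, might help choose patients for phase II.

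**The concern.** Significance is the only statistical filter between an exome-wide list and a set of candidates for development, and the plan leaves it undefined. An exome screen tests many variants in very few subjects. At a conventional unadjusted level, many would pass by chance imbalance between responders and non-responders.

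The one later step in the plan works on the same DNA. It can remove a miscalled variant. It leaves a correctly called variant with a chance association exactly as it was. The documents neither name nor require an independent replication cohort.

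At stake is the content of the candidate list. If it informs phase II patient selection, as Section 4.2.3.2 allows, it may consist mostly or wholly of chance findings, and nothing in the report would show how many to expect.

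**Working it through.** The plan gives no error rate, number of variants or power for this analysis, so there is no figure to reproduce. The calculation below is illustrative.

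**Inputs from the documents.** 15 planned subjects (Section 5.8), taken as the upper limit on trial subjects sequenced. Pearson or Spearman correlation of mutation presence with outcome (Section 10.1).

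**Assumptions, none stated in the documents.** All 15 are sequenced; 7 respond and 8 do not; two-sided 0.05 per variant, unadjusted; carrier frequency uniform over 5–50%, 10–50% or 20–60%; 1,000 or 20,000 variants tested. Fisher's exact test is added as a reference.

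**Step 1. Chance that a null variant with k carriers is selected.** The number of carriers among responders, a, is hypergeometric:

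P(a) = C(7,a) × C(8,k−a) / C(15,k), summed over the values of a for which the test gives p ≤ 0.05.

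Example, k = 7, Fisher: a = 0, 1, 6 and 7 reject, so (8 + 196 + 56 + 1)/6435 = 261/6435 = 0.0406.

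Example, k = 3: with a = 3 the probability is C(7,3)/C(15,3) = 35/455 = 0.0769. Pearson's p-value falls below 0.05 here; Fisher's does not.

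| Carriers among 15 | Fisher | Pearson |
|---|---|---|
| 0–2 or 13–15 | 0 | 0 |
| 3 or 12 | 0 | 0.0769 |
| 4 or 11 | 0.0256 | 0.0769 |
| 5 or 10 | 0.0256 | 0.0256 |
| 6–9 | 0.0406 | 0.0406 |

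Spearman's coefficient equals Pearson's when both variables are binary.

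**Step 2. Average over carrier counts**, with k binomial (15, q) and q uniform over each range:

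| Range of q | Fisher | Pearson |
|---|---|---|
| 5–50% | 0.0184 | 0.0361 |
| 10–50% | 0.0206 | 0.0397 |
| 20–60% | 0.0278 | 0.0435 |

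Per 1,000 null variants this is 18 to 28 (Fisher) or 36 to 43 (Pearson). Per 20,000 it is about 368 to 556 (0.01839 and 0.02782 × 20,000) or 722 to 870 (0.03610 and 0.04348 × 20,000). At a 5/10 split the same formula gives 16 to 22 (Fisher) or 45 to 49 (Pearson) per 1,000, so the finding does not hang on 7/8.

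**Step 3. Effect of the Sequenom step.** For a correctly called variant, the table of carriers by response is the same after re-genotyping, so its p-value is the same. The counts in Step 2 do not change.

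**Step 4. What an adjusted screen could declare.** The smallest exact p at a 7/8 split is 1/C(15,7) = 1/6435 = 0.000155.

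- *Bonferroni at 5%:* 0.05 × 6435 = 321.75, so no variant can pass once more than 321 are tested. The limit is 150 at a 5/10 split and 22 at 3/12. With 12 subjects split 5/7 it is 39.
- *Benjamini-Hochberg at 5% over 20,000 variants:* declaring m variants needs the m-th smallest p to be at most m × 0.05/20,000. Since no p is below 1/6435, m must be at least 20,000/(0.05 × 6435) = 62.2, that is 63 variants at the minimum. Only variants with 7 or 8 carriers can reach it. Even if all 20,000 were null and of that kind, about 20,000/6435 = 3.1 would be expected there.

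**The case against.** **The validation wording.** A reader might infer from "Variants associated with response/no response will be then validated in the discovery cohort using sequenome analysis" that the plan claims to validate the association in the subjects who generated it. The documents do not support that. The same sentence gives the purpose as confirming that the variants exist in the sampled DNA. Using the same DNA is right for that, and the mention of replicating suggests that replication is a separate matter. What remains is that this step cannot stand in for control of chance findings, and nothing else in the plan supplies it.

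**Candidates, not biomarkers.** A reader might also infer that selected variants become biomarkers or entry criteria. The appendix makes them targets for development, attaches that wording to variants outside the literature genes, and sets no rule by which a variant gates enrolment. Section 4.2.3.2 is conditional. This limits the harm.

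**Status and numbers.** The objective is exploratory and conditional on funding, and Section 5.8 concedes that the sample is small. Appendix F refers to a separate DNA-collection protocol, which may hold analysis details that are not visible here, and it gives no number sequenced. All of this stands. Fifteen is inferred, and if only trial subjects with complete data are sequenced, fewer would make Step 4 tighter. Exploratory status lowers the stakes but does not define a rule that the plan itself states in terms of significance.

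**The remedy may return nothing.** Step 4 confirms this for the exome-wide family. Ranking candidates with estimates is a defensible output for so small a screen, and the fix includes it.

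**Conclusion.** The concern holds in a limited form. Appendix F selects variants by significance without defining it, Section 10.1 adds no control across variants, and the technical check on the same DNA removes no chance association. With 15 subjects, a 7/8 split, unadjusted two-sided 0.05 and carrier frequencies between 5% and 60%, about 18 to 28 null variants per 1,000 would be selected by Fisher's test or 36 to 43 by Pearson correlation. The number sequenced, split, level, frequencies and number tested are all assumptions; the direction of the result does not depend on their exact values. Severity is minor, because no primary or secondary conclusion depends on this objective.

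**What to change.** In Appendix F, Objective 2, with a matching line in Section 10.1:

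1. Replace the significance wording with a stated rule. Test literature-gene variants as one family, listed before the data are seen, and all other variants as a second. Control the false discovery rate within each family by permutation or Benjamini-Hochberg. Use exact or permutation p-values, since Pearson's rejects too often at some carrier counts (0.0769 against a nominal 0.05).
2. State the response time point used. Section 10.1 lists four, Objective 2 names none, and repeating the screen over them would add to the multiplicity.
3. Report estimates and ranks for all variants tested, with the number tested in each family.
4. Call every hit hypothesis-generating until it is tested in independent samples, and before any use in phase II patient selection.

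The Sequenom step can stay as it is.

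**Cost.** A few sentences and a routine adjustment, with no added patients, visits or assays. The real price is that the exome-wide family may yield no declared hits at this sample size. A short literature-gene list has a better chance, and the ranked estimates remain as input to later work.
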